4.8.6.4 Vital signs

Observed values at baseline and observed and change from baseline values for post-baseline visits will be summarised for each vital sign. A figure with line plots of the mean change from baseline (+/- SE) of selected vital signs parameters (SBP, DBP and pulse) will be provided. Additionally, a qualitative summary over time of vital signs results will be provided for SBP, DBP, pulse and temperature with categories low, normal and high assigned per the AstraZeneca-defined reference ranges for vital signs (Appendix B). A shift table from baseline to minimum value post-baseline for each parameter (SBP, DBP, pulse, temperature) will be summarised. Similarly, a shift table from baseline to maximum value post-baseline for each parameter will be summarised.

Observed values will be listed and values outside AstraZeneca defined reference ranges and clinically significant change criteria (see Appendix B AstraZeneca defined reference ranges for vital signs) will be flagged. If both the baseline and post-baseline values of a parameter are beyond the same limit for that parameter, then the post-baseline value only will be flagged if it is more extreme (farther from the limit) than the baseline value. If the baseline value is beyond the low, and the post-baseline value is beyond the high limit (or vice-versa), then the post-baseline value will be flagged. If the baseline value is not beyond either limit, and the post-baseline value is beyond either limit, then the post-baseline value will be flagged.

Sitting and supine results for vital signs will not be summarised separately. All results will be summarised together regardless of position (e.g. "diastolic blood pressure" could include both supine and sitting results).

4.8.6.5 ECG variables

A shift table from baseline to last observation post-baseline for ECG evaluation (normal, abnormal - not clinically significant, abnormal - clinically significant, and not done) will be summarised and all results listed for each ECG performed.

4.8.6.6 Physical examinations

As any clinically relevant abnormal medical findings should be recorded on the medical history or AE form if the finding was reported during the experimental phase of the study, no physical examination data will be listed.

5. INTERIM ANALYSES

No interim analysis specific to this study will be conducted.

6. CHANGES OF ANALYSIS FROM PROTOCOL

Table 2 Summary of changes from protocol

Reference	Protocol	Change	Justification
SAP Section 1.1.4	Section 2.4.	
The following exploratory endpoints will be included:
 
• European League Against Rheumatism (EULAR) response criteria.• DAS28 remission.• Clinically important change.• Low disease activity.	Additional endpoints considered important for efficacy interpretation by study team.
SAP Section 1.3	Section 8.2.	
Comparison to traditional hypothesis testing has been removed and replaced with a statement that the study is “not sufficiently powered to support hypothesis testing”.
 
The sample size of “n=18” per arm has been updated to “n=10” per arm.
	
Power of the study expected to be lower than that stated in the protocol, given the sample size and expected effect size. Wording updated to remove power calculation.
 
Update to n reflects agreement to close recruitment early. Hence a reduced n per arm was agreed.

SAP Section 4.2.1	Section 8.5.1	Concluded that the difference in mean CFB in DAS28 of AZD9567 - mean CFB in DAS28 of Prednisolone will show a better efficacy if the observed difference negative (less than 0) instead of positive (larger than 0).	Lower DAS28 score is better.

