8.2 Sample size estimate

This study, is a Phase IIa study, where the aim is to show that the efficacy of AZD9567 is equivalent to the efficacy of prednisolone 20 mg. The design is a two arm design, one arm receiving prednisolone 20 mg and the other receiving AZD9567.

The endpoint proposed is the change from baseline (CFBL) in DAS28 units for each patient. The main analysis will be based on the difference $X_T - X_P$, between X_T , the average change from base line of the chosen dose of AZD9567 and, X_P , the mean CFBL of prednisolone 20 mg. Therefore, this difference quantifies the treatment effect i.e. how much better AZD9567 is compared to prednisolone 20 mg in terms of average CFBL in DAS28 units.

The details of the sample size calculation are based on internal decision criteria as explained in [Frewer et al, 2016](#). In these calculations we use the reliability threshold of the DAS28 index known to be 0.6 ([Siemons et al, 2014](#)).

Using a sample size of 18 per arm, results in good decision criteria. In comparison with traditional hypothesis testing this corresponds to a test with significance level $\alpha=0.09$ and $\beta=0.10$.

The above results have been evaluated using simulations. Further details of the statistical methodology will be outlined in the SAP.

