8.5 Methods for statistical analyses

8.5.1 Analysis of the primary variable(s)

To show that the efficacy of AZD9567 is equivalent to the efficacy of p20 mg in terms of change from baseline in DAS28, we will use the difference in DAS28 units, $X_T - X_p$, between, X_T , the average CFBL of the chosen dose of AZD9567 and, X_p , the mean CFBL of prednisolone 20 mg. This difference will be calculated using a mixed model. It will be concluded that the data support better efficacy of AZD9567 whenever the observed difference is positive (larger than 0). Similarly, it will be concluded that the AZD9567 is less efficacious than prednisolone 20 mg if the difference is negative (less than -0.4). Formal statistical testing will be performed for exploratory purposes only.

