4.2 Analysis methods for efficacy variables

4.2.1 Primary efficacy variable analysis method

The difference in change from baseline in DAS28 between AZD9567 and prednisolone (AZD9567 – prednisolone) will be calculated using a mixed model.

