4.4 Missing primary and secondary variables

4.4.1 Missing DAS28 (CRP) components

DAS28-CRP will be set to be missing if one or more components as defined above are missing. Higher DAS28-CRP scores indicate more severe symptoms and greater functional impairment

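### The SAP reverses the sign of the 'better efficacy' rule but leaves the protocol's 'less efficacious below -0.4' rule standing, so both conclusions fall on the same side of zero

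*SAP*

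**What the plan says.** **Direction of the difference.** Protocol 8.2 and 8.5.1 define it as the mean change on AZD9567 minus the mean change on prednisolone 20 mg. SAP 3.1 keeps that order, and so does SAP 4.2.1: "The difference in change from baseline in DAS28 between AZD9567 and prednisolone (AZD9567 – prednisolone) will be calculated using a mixed model".

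**Direction of the scale.** SAP 4.4.1: "Higher DAS28-CRP scores indicate more severe symptoms and greater functional impairment". SAP 3.5.2 defines improvement as post-baseline minus baseline. On the SAP's terms, a negative difference therefore favours AZD9567.

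**The protocol rule (8.5.1)** has two halves. The data are taken to support "better efficacy of AZD9567 whenever the observed difference is positive (larger than 0"). The second half reads: "it will be concluded that the AZD9567 is less efficacious than prednisolone 20 mg if the difference is negative (less than -0.4").

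**The SAP change (Section 6, Table 2, row for SAP 4.2.1 against protocol 8.5.1).** The difference "will show a better efficacy if the observed difference negative (less than 0) instead of positive (larger than 0"). The reason given is that a lower DAS28 is better. No row deals with the -0.4 cut-off.

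**Where the rule is meant to be.** SAP 4.2.1 says only that the difference "will be calculated using a mixed model". SAP 4.3.1 gives the model, confidence intervals and exploratory p-values. Neither contains a decision rule.

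**The concern.** The protocol's two halves share one sign convention, in which positive is favourable. The SAP moves to the opposite convention but carries over only one half. Its stated reason applies just as much to the -0.4 cut-off, yet that sentence remains as current protocol text.

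The rule matters because nothing else in the plan leads to a primary conclusion. Protocol 8.1 says efficacy is to be assessed with the decision framework and that formal tests are exploratory. SAP 1.3 says 10 per group is not enough to support hypothesis testing. If the rule contradicts itself on one side of zero and is silent on the other, the missing cut-off will have to be inferred by whoever writes the report, possibly with the result in view.

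**Working it through.** **1. The rules side by side.** D is the observed difference, AZD9567 minus prednisolone.

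| Observed D | Protocol 8.5.1 alone | SAP Table 2 plus the unamended protocol sentence | Both halves mirrored |
|---|---|---|---|
| -1.0 | less efficacious | better **and** less efficacious | better |
| -0.6 | less efficacious | better **and** less efficacious | better |
| -0.4 | none | better | better |
| -0.2 | none | better | better |
| 0 | none | none | none |
| +0.2 | better | none | none |
| +0.4 | better | none | none |
| +0.6 | better | none | less efficacious |
| +1.0 | better | none | less efficacious |

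The first and last columns each give mutually exclusive conclusions. The first has an indeterminate band from -0.4 to 0, and the last has its mirror image from 0 to +0.4. The middle column overlaps everywhere below -0.4 and has no adverse conclusion that stands alone. No single sign convention produces the middle column.

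**2. The plan's own sample-size figure.** Protocol 8.2 gives 18 per arm with alpha 0.09, beta 0.10 and a threshold of 0.6, but no SD, so the figure cannot be reproduced. If 0.6 is taken as the difference to detect, the implied SD is 0.6 × √(18/2) / (z for alpha + z for power):

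- one-sided: 1.8 / (1.341 + 1.282) = 0.686
- two-sided: 1.8 / (1.695 + 1.282) = 0.605

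These values only help to place the SD range used next.

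**3. How often each conclusion would arise.**

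Inputs:
- n = 10 per arm (SAP 1.3)
- cut-offs 0 and -0.4 (SAP Table 2 and protocol 8.5.1)
- true differences of ±0.6, the DAS28 reliability threshold in protocol 8.2
- SD of DAS28 change 0.7, 1.0 or 1.3 (**assumption**)
- D approximately normal, with SE = SD × √(2/10)

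| Quantity | Formula | SD 0.7 | SD 1.0 | SD 1.3 |
|---|---|---|---|---|
| SE | SD × 0.4472 | 0.313 | 0.447 | 0.581 |
| True +0.6: D < -0.4, flagged less efficacious (and also better) | Φ(-1.0/SE) | 0.0007 | 0.013 | 0.043 |
| True +0.6: D ≥ 0, no conclusion | Φ(0.6/SE) | 0.972 | 0.910 | 0.849 |
| True +0.6: D > +0.4, flagged under the mirrored rule | Φ(0.2/SE) | 0.739 | 0.673 | 0.635 |
| True -0.6: D < -0.4, both conclusions | Φ(0.2/SE) | 0.739 | 0.673 | 0.635 |
| True 0: D < -0.4, both conclusions | Φ(-0.4/SE) | 0.101 | 0.186 | 0.246 |

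**The case against.** **The SAP may replace protocol 8.5.1 altogether.** It never repeats the -0.4 sentence, so the contradiction depends on reading an amended SAP line together with an unamended protocol line. However, the SAP does not say that it replaces the section, and Table 2 presents itself as a list of changes, so an unlisted sentence stands. If replacement was intended, the overlap disappears but no 'less efficacious' criterion remains. An observed deficit leads to no conclusion on either reading.

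**The protocol may have meant improvement by change from baseline.** Protocol 8.2 says the difference measures how much better AZD9567 is, and with positive improvement scores both original halves are coherent. The protocol alone cannot exclude this. It does not rescue the combined rule, because the SAP has fixed the opposite sign and changed only one half.

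**The rule acts on the observed difference, not the true one.** This is correct. With a true deficit of 0.6, the observed difference is below zero in about 3% to 15% of trials (1 minus the no-conclusion row), and those trials would be called better. The statement that a deficit triggers nothing holds strictly for observed differences of zero or more.

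**The practical effect may be small.** SAP 4.3.1 reports the estimate, interval and p-value whatever the rule says, and a careful reader would see which direction was intended. The estimate would indeed be visible. The cut-off on the unfavourable side would still be chosen by inference, which pre-specification is meant to prevent.

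**Neither document states +0.4.** This stands. Mirroring follows from the SAP's own reason, but the sponsor must confirm the value.

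**Conclusion.** The concern holds. As written, the primary decision rule gives two opposite conclusions for any observed difference below -0.4 and none for any difference of zero or more. That is a matter of logic and needs no assumption beyond reading the SAP as amending only what it lists.

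The frequencies do rest on assumptions: an SD of 0.7 to 1.3, 10 per arm and a normal approximation. On that basis a true deficit of 0.6 is flagged in 0.07% to 4.3% of trials (1.3% at SD 1.0), against 63% to 74% (67% at SD 1.0) with a mirrored cut-off. A true benefit of 0.6 draws the 'less efficacious' label in 63% to 74%. The estimate and its interval are unaffected; the error lies in the conclusion drawn from them. Because the plan judges efficacy by this framework rather than by a test, it must be corrected.

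**What to change.** Write the whole rule into SAP 4.2.1 under one sign convention: the difference is AZD9567 minus prednisolone in post-baseline minus baseline DAS28, and negative values favour AZD9567. AZD9567 is better below 0 and less efficacious above +0.4, subject to the sponsor confirming +0.4 as the intended mirror of the protocol's cut-off. State that values from 0 to +0.4 are indeterminate, as the band from -0.4 to 0 was in the protocol. Add the reversal of the -0.4 cut-off to Table 2, and say there that the new rule replaces both sentences of protocol 8.5.1.

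The cost is a few lines of SAP text, which should be settled before unblinding. No data collection, model or programming changes.
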